 - Uncontrolled angina within the 3 months prior to consent
 - Any history of clinically significant arrhythmias (such as ventricular tachycardia, ventricular fibrillation, torsades de pointes or poorly controlled atrial fibrillation)
 - QTc prolongation > 480 msec
 - History of other clinically significant cardiovascular disease (ie, cardiomyopathy, congestive heart failure with New York Heart Association functional classification III-IV, pericarditis, significant pericardial effusion, significant coronary stent occlusion, poorly controlled deep venous thrombosis, etc)
 - Cardiovascular disease-related requirement for daily supplemental oxygen
 - History of 2 or more MIs OR 2 or more coronary revascularization procedures
 - Participants with history of myocarditis, regardless of etiology

- Left ventricular ejection fraction (LVEF) < 50% by either transthoracic echocardiogram (TTE) or multiple gated acquisition (MUGA) scan (TTE is preferred test) within 6 months prior to date of first study drug administration.
- Troponin T (TnT) or I (TnI) > 2 × institutional upper limit of normal (ULN). Participants with TnT or TnI levels between > 1 to 2 × ULN will be allowed to enroll if a repeat assessment remains within ULN or patient has no cardiac symptoms and participant undergoes a cardiac imaging evaluation found to have no significant myocardial disease or dysfunction. When repeat levels within 24 hours are not available, a repeat test should be conducted as soon as possible.

Objectives and Endpoints:

Objective	Endpoint
Primary	

 • To compare objective response rate (ORR) of BMS-986213 in combination with chemotherapy, with ORR of nivolumab in combination with chemotherapy, by BICR, in randomized participants with untreated, unresectable, and either locally advanced or metastatic LAG-3 positive GC or GEJ adenocarcinoma. 	
 • ORR in participants who are LAG-3 positive. ORR is defined as the number of participants with a best overall response (BOR) of CR or PR divided by the number of randomized participants in each arm. BOR is defined as the best response designation as determined by the blinded independent central review (BICR), recorded between the date of randomization and the date of objectively documented progression (per Response Evaluation Criteria in Solid Tumors [RECIST 1.1]), death due to any cause, or the date of subsequent anti-cancer therapy, whichever occurs first.
Secondary	

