4 OBJECTIVES AND ENDPOINTS

[figure not shown]
Table 4-1: Objectives and Endpoints

Objective	Endpoint
Primary	

 To compare ORR of BMS-986213 in combination with chemotherapy, with ORR of nivolumab in combination with chemotherapy, by BICR, in randomized participants with untreated, unresectable, and either locally advanced or metastatic LAG-3 positive GC or GEJ adenocarcinoma. 	
 ORR in participants who are LAG-3 positive. ORR is defined as the number of participants with a BOR of CR or PR divided by the number of randomized participants in each arm. BOR is defined as the best response designation as determined by the BICR, recorded between the date of randomization and the date of objectively documented progression (per Response Evaluation Criteria in Solid Tumors [RECIST 1.1]), death due to any cause, or the date of subsequent anticancer therapy, whichever occurs first.
Secondary	

 To assess the overall safety and tolerability of BMS-986213 in combination with chemotherapy vs. nivolumab in combination with chemotherapy in treated participants with advanced or metastatic GC or GEJ cancer. To compare ORR of BMS-986213 in combination with chemotherapy, with ORR of nivolumab in combination with chemotherapy, as assessed by investigator, in randomized participants with untreated, unresectable, and either locally advanced or metastatic LAG-3 positive GC or GEJ adenocarcinoma. To compare ORR by BICR and by investigator of BMS-986213 in combination with chemotherapy with ORR of nivolumab in combination with chemotherapy in randomized participants with advanced or metastatic LAG-3 negative GC or GEJ adenocarcinoma, and overall (across LAG-3 negative and positive groups). 	
 The incidence of AEs, SAEs, AE leading to discontinuation, deaths, and laboratory abnormalities in each arm. ORR is defined as above, as the number of participants with a BOR of CR or PR as assessed by the investigator using RECIST 1.1, divided by the number of randomized participants in each Treatment Arm. ORR in the LAG-3 negative group or overall is defined as above, as the number of participants in each population with a BOR of CR or PR divided by the number of randomized participants in each Treatment Arm, for that population.

Table 4-1: Objectives and Endpoints

Objective	Endpoint

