10.3.2 Efficacy Analyses

Primary Endpoint	Statistical Analysis Methods

 Objective response rate (ORR) as assessed by BICR in participants who are LAG-3 positive is defined as the number of participants with a best overall response (BOR) of CR or PR divided by the number of randomized participants who are LAG-3 positive in each arm. BOR is defined as the best response designation based on the BICR, recorded between the date of randomization and the date of objectively documented progression (per RECIST 1.1 as determined by the investigator) or death, or the date of subsequent anti-cancer therapy, whichever occurs first. 	
 ORR as assessed by BICR in participants who are LAG-3 positive will be compared between the BMS-986213 in combination with chemotherapy and nivolumab in combination with chemotherapy using a two-sided Cochran-Mantel-Haenszel test stratified by region (J/T or ROW) and PD-L1 status (CPS < 1 or indeterminate, CPS ≥ 1 to <5, CPS ≥ 5) as recorded in the IRT. Associated 70% CIs for ORR difference will be calculated. Additionally, ORR along with the exact 95% CI for each arm will be calculated using the Clopper-Pearson method.⁵²
Secondary	

 Objective Response Rate (ORR) as assessed by investigator in participants who are LAG-3 positive is defined as the number of participants with a best overall response (BOR) of CR or PR divided by the number of randomized participants who are LAG-3 positive in each arm. BOR is defined as the best response designation based on the investigator, recorded between the date of randomization and the date of objectively documented progression (per RECIST 1.1) or the date of subsequent anti-cancer therapy, whichever occurs first. 	
 ORR based on investigator in LAG-3 positive population will be compared between the BMS-986213 in combination with chemotherapy vs Nivolumab in combination with chemotherapy using a two-sided Cochran-Mantel-Haenszel test stratified by region (J/T ROW) and PD-L1 status as recorded in the IRT. Additionally, ORR along with the exact 95% CI for each arm will be calculated using the Clopper-Pearson method.⁵²

Primary Endpoint	Statistical Analysis Methods

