3 OBJECTIVES

Table 3-1: Objectives and Endpoints

Objectives	Endpoints
Primary Objective:	
To compare ORR of BMS-986213 in combination with chemotherapy, with ORR of nivolumab in combination with chemotherapy, by BICR, in randomized subjects with untreated, unresectable, and either locally advanced, or metastatic LAG-3 positive GC or GEJ adenocarcinoma.	ORR in subjects who are LAG-3 positive. ORR is defined as the number of subjects with a BOR of CR or PR divided by the number of randomized subjects in each arm. BOR is defined as the best response designation as determined by the BICR, recorded between the date of randomization and the date of objectively documented progression (per Response Evaluation Criteria in Solid Tumors [RECIST 1.1]), death due to any cause, or the date of subsequent anticancer therapy, whichever occurs first.
Secondary Objectives:	
To assess the overall safety and tolerability of BMS-986213 in combination with chemotherapy vs. nivolumab in combination with chemotherapy in treated subjects with advanced or metastatic GC or GEJ cancer.	The incidence of AEs, SAEs, AE leading to discontinuation, deaths, and laboratory abnormalities in each arm.
To compare ORR of BMS-986213 in combination with chemotherapy, with ORR of nivolumab in combination with chemotherapy, as assessed by investigator, in randomized subjects with untreated, unresectable, and either locally advanced, or metastatic LAG-3 positive GC or GEJ adenocarcinoma.	ORR is defined as above, as the number of subjects with a BOR of CR or PR as assessed by the investigator using RECIST 1.1, divided by the number of randomized subjects in each Treatment Arm.
To compare ORR by BICR and by investigator of BMS-986213 in combination with chemotherapy with ORR of nivolumab in combination with chemotherapy in randomized subjects with advanced or metastatic LAG-3 negative GC or GEJ	ORR in the LAG-3 negative group or overall is defined as above, as the number of subjects in each population with a BOR of CR or PR divided by the number of randomized

Table 3-1: Objectives and Endpoints

Objectives	Endpoints
adenocarcinoma, and overall (across LAG-3 negative and positive groups).	subjects in each Treatment Arm, for that population

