4.1.1 Objective Response Rate

Objective Response Rate (ORR) is defined as the number of randomized subjects who achieve a best response of confirmed complete response (CR) or confirmed partial response (PR) based on BICR assessments (using RECIST v1.1 criteria) divided by the number of all randomized subjects. If the objective is for a particular population (LAG3 positive, LAG3 negative), only that population is selected. Best Overall Response (BOR) is defined as the best response, as determined by the BICR, recorded between the date of randomization and the date of objectively documented progression per RECIST v1.1 criteria or the date of subsequent therapy (including tumor-directed radiotherapy and tumor-directed surgery), whichever occurs first. For subjects without documented progression or subsequent therapy, all available response designations will contribute to the BOR determination. Confirmation of response is required at least 4 weeks after the initial response.

When the objective is specific to the investigator assessment, the above definition is altered to exchange BICR for investigator assessment in the derivation of the endpoint.

Time to Response

Time to Response (TTR) is defined as the time from randomization to the date of the first confirmed documented response (CR or PR), as assessed by the BICR. TTR will be evaluated for responders (confirmed CR or PR) only.

When the objective is specific to the investigator assessment, the above definition is altered to exchange BICR for investigator assessment in the derivation of the endpoint.

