4.1.2 Duration of Response

Duration of Response (DOR) is defined as the time between the date of first confirmed documented response (CR or PR) to the date of the first documented tumor progression as determined by the BICR (per RECIST v1.1 criteria), or death due to any cause, whichever occurs first. Subjects who start subsequent therapy without a prior reported progression will be censored at the last evaluable tumor assessments prior to initiation of the subsequent anticancer therapy. Subjects who die without a reported prior progression will be considered to have progressed on the date of their death. Subjects who neither progress nor die, DOR will be censored on the date of their last evaluable tumor assessment. DOR will be evaluated for responders (confirmed CR or PR) only.

[REDACTED]

When the objective is specific to the investigator assessment, the above definition is altered to exchange BICR for investigator assessment in the derivation of the endpoint.

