7.5 Efficacy

Principal analyses of objective response rate (ORR) and progression free survival (PFS) will be based on the Blinded Independent Central Review (BICR) evaluation, unless noted otherwise.

Unless stated otherwise, whenever a stratified analysis is specified in the all randomized population, the following stratifications factors (recorded at randomization as per IRT) will be used, except for the analysis in LAG-3 positive or LAG-3 negative sub-groups when only PDL1 CPS expression will be used.

- LAG-3 expression ($\geq 1\%$ or $< 1\%$; no indeterminate allowed)
- PD-L1 expression status (CPS ≥ 5 , CPS ≥ 1 to < 5 , CPS < 1 or indeterminate)

There will be no p-values presented for any of the analyses other than the primary endpoint. All other analyses will be descriptive in nature. Confidence intervals for all endpoints will be at the two-sided 95% level. Point estimates and confidence bounds for efficacy variables will be rounded to the second decimal place.

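### Protocol 10.3.2 ends the blinded-review response window for the primary endpoint at the investigator's progression call, and no other definition says whose progression counts

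*Protocol*

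**What the plan says.** In the primary-endpoint row of protocol 10.3.2, best overall response comes from BICR. The window runs from randomization to "the date of objectively documented progression (per RECIST 1.1 as determined by the investigator) or death", or to subsequent anti-cancer therapy if that is earlier. In the same table, the row for investigator-assessed response refers only to progression per RECIST 1.1 and names no assessor. The only explicit mention of investigator progression in a response definition is therefore on the BICR endpoint.

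The other definitions of the primary best response name BICR for the response but nobody for the progression that ends the window:

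- Protocol synopsis: "as determined by the blinded independent central review (BICR), recorded between the date of randomization and the date of objectively documented progression".
- Protocol Table 4-1: the window ends at "the date of objectively documented progression (per Response Evaluation Criteria in Solid Tumors [RECIST 1.1]), death due to any cause" or subsequent therapy.
- SAP Table 3-1: "as determined by the BICR, recorded between the date of randomization and the date of objectively documented progression".
- SAP 4.1.1: "as determined by the BICR, recorded between the date of randomization and the date of objectively documented progression per RECIST v1.1 criteria".

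For investigator endpoints, SAP 4.1.1 adds that "the above definition is altered to exchange BICR for investigator assessment in the derivation of the endpoint". SAP 7.5 says "Principal analyses of objective response rate (ORR) and progression free survival (PFS) will be based on the Blinded Independent Central Review (BICR) evaluation". For duration of response, SAP 4.1.2 does name the assessor: the end date is "the date of the first documented tumor progression as determined by the BICR (per RECIST v1.1 criteria") or death.

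**The concern.** Treatment is known to the investigator, and blinded review is what keeps knowledge of the arm out of the primary endpoint. Under the wording of 10.3.2, an unblinded progression call that BICR did not confirm can turn a blinded responder into a non-responder. The primary endpoint is also the only analysis for which SAP 7.5 plans a p-value.

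There is a practical problem too. A programmer following protocol 10.3.2 and one reading SAP 4.1.1 as BICR throughout could produce different responder counts from the same data. The cross-tabulation of BICR against investigator best response planned in SAP 7.5.1 would show disagreement between assessors. It would not show what the choice of cut-off does to the primary result.

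**Working it through.** The documents give no figure to reproduce here. The check compares the definitions, works out who could be affected, and then sets a scale.

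**1. Definitions side by side**

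| Source | Response assessed by | Progression that ends the window or duration |
|---|---|---|
| Protocol 10.3.2, primary ORR | BICR | Investigator |
| Protocol 10.3.2, investigator ORR (LAG-3 positive) | Investigator | Not named |
| Protocol synopsis and Table 4-1, primary | BICR | Not named |
| Protocol Appendix 5, 2.3.1 | Not named | Not named |
| SAP Table 3-1 and 4.1.1, primary | BICR | Not named |
| SAP 4.1.2, duration of response | BICR | BICR |
| SAP 4.1.3.1, PFS | BICR | BICR |

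**2. Who could be classified differently**

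A participant's status can change only if all of these hold:

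- the investigator has called progression;
- BICR has not called progression by then;
- no subsequent therapy has started, since that closes the window under either reading;
- scanning continues;
- the BICR response was not already confirmed.

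The plan provides for such participants. Protocol 7.3.8 allows treatment beyond investigator progression, with a scan within 6 weeks. Protocol 9.1.4 keeps participants on scans, if clinically feasible, when BICR does not confirm progression.

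**3. How it could happen**

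Protocol 9.1.3 requires confirmation at least 28 days after first response. On the protocol's schedule, scans are every 42 days up to Week 48. Nothing scheduled falls between two adjacent scans, so the ordinary gap between response and confirmation creates no exposure by itself. The main paths are an unconfirmed investigator progression call:

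- (a) at or before the first BICR response scan;
- (b) on the one intervening time point that Appendix 5, 2.3.4 permits before confirmation. This spans 2 × 42 = 84 days, or 70 to 98 days with a ±7-day window at each end;
- (c) on an unscheduled scan, which protocol 9.1.1 sends to BICR.

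The documents do not say whether a scan on the closing date itself counts. If the investigator calls progression on the confirming scan, the outcome depends on that as well.

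**4. Scale (illustration only)**

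The LAG-3 positive sample size is redacted. Assume n = 40 to 125 per arm, where 125 is half of the 250 randomized and so the ceiling, and a response rate p of 40 to 60% in both arms. One net reclassified responder shifts the difference by 1/n. The unstratified 70% half-width is 1.0364 × √(2p(1−p)/n).

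| n per arm | Half-width (points) | Shift 1/n (points) | Shift as share of half-width |
|---|---|---|---|
| 40 | 11.35–11.59 | 2.50 | 21.6–22.0% |
| 62 | 9.12–9.31 | 1.61 | 17.3–17.7% |
| 75 | 8.29–8.46 | 1.33 | 15.8–16.1% |
| 125 | 6.42–6.55 | 0.80 | 12.2–12.5% |

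Protocol 10.3.2 and SAP 7.5.1 name a 70% interval for the difference, while SAP 7.5 says all intervals are 95%. A 95% interval is 1.96/1.0364 = 1.89 times as wide, so the shares become about 6.5 to 11.6%. With no net reclassification the shift is zero.

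**The case against.** The strongest reply is that the SAP already settles the matter in substance. It is the later and more detailed analysis document (version 2, July 2020). It drops the protocol's reference to the investigator, exchanges one assessor for the other across a whole derivation, bases the principal response analysis on BICR, and uses BICR progression for duration of response and PFS. BICR is the natural reading. That stands, but the reading is only implied. It contradicts an explicit protocol sentence on the primary endpoint, and the SAP does not record the departure. By contrast, the SAP does explain why region is dropped as a stratification factor.

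Other points also carry weight:

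- Few participants can be affected, no effect has been shown, and a shift of 1/n describes any single reclassified participant whatever the cause. This is accepted, and the figures above are a scale, not an estimate.
- A response confirmed before investigator progression can have its duration run to a later BICR progression without contradiction. Also correct: SAP 4.1.2 matters because it shows the SAP naming the assessor elsewhere, not because it conflicts.
- Read alone, 10.3.2 sets no cut-off at BICR progression when the investigator has called none. Appendix 5, 2.3.1 ends best response at disease progression, so a BICR reading would ordinarily stop there. This weakens that side of the problem but leaves the investigator cut-off in place.
- The BICR charter, to which both documents defer for procedures, was not available and may fix the rule. If so, the SAP should say so.

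**Conclusion.** The concern holds. Current protocol text for the primary endpoint pairs a BICR response with an investigator cut-off, and no other passage expressly overrides it. This should be fixed, though nothing shows that it would change the result.

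The contradiction in the text is certain. Its numerical effect is not: size and direction are unknown and may be zero, and the documents give no basis for a count of affected participants. Equal loss in both arms under equal true response rates would create no difference. The illustration of 0.8 to 2.5 points per net reclassified responder rests on the assumed sample sizes, and its share of the interval half-width also rests on the assumed response rates and an unstratified standard error.

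**What to change.** In SAP 4.1.1 and Table 3-1, state that the progression closing the window for the primary endpoint is BICR-assessed, as SAP 4.1.2 already does for duration of response, and note the departure from protocol 10.3.2. Use investigator progression as the cut-off only for investigator-assessed response. This SAP wording alone settles the analysis.

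Correct 10.3.2 to BICR at the next amendment or by administrative letter. Under protocol Appendix 2, an amendment needs IRB/IEC approval and a letter requires that the IRB/IEC be informed.

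Optionally, report BICR response truncated at investigator progression as a sensitivity analysis, with the number per arm whose best response changes. That is one extra table.

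No new data are needed, because BICR progression is already derived for duration of response and PFS. The change reduces investigator influence but does not remove it: subsequent therapy started after an investigator progression call still closes the window.

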10.3.3 Safety Analyses

All safety analyses will be performed on the Safety Sample.

Endpoint	Statistical Analysis Methods

Secondary
 
The Safety and tolerability objective will be measured by the incidence of adverse events (AEs), serious adverse events (SAEs), adverse events leading to discontinuation, deaths, and laboratory abnormalities in each arm by LAG-3 group and overall	
Safety analyses will be performed in all treated participants. Descriptive statistics of safety will be presented using National Cancer Institute (NCI) Common Terminology Criteria for Adverse Events (CTCAE) version 5.0 by treatment group. All on-study AEs, treatment-related AEs, SAEs, and treatment-related SAEs will be tabulated using worst grade per NCI CTCAE v 5.0 criteria by system organ class and preferred term. On-study lab parameters including hematology, chemistry, liver function, and renal function will be summarized using worst grade NCI CTCAE v 5.0 criteria.

[figure not shown]
10.3.9 Interim Analyses

[figure not shown]
There are no official planned interim analyses. Approximately after at least 24 weeks since the last participants has been randomized, or after all randomized participants had an opportunity to complete at least 24-week scans, the ORR analysis will be performed. Additional analyses that allow for longer follow-up to estimate the DOR and other time to event endpoints will also be performed, after at least 9 months since the last participant has been randomized. In addition planned analyses will be produced for DMC evaluation of risk/benefit, as per the DMC charter.

[figure not shown]

[figure not shown]

12 APPENDICES

APPENDIX 1 ABBREVIATIONS AND TRADEMARKS

Term	Definition
1L	first-line
5-FU	5-fluorouracil
AE	adverse event
ALT	alanine aminotransferase
AST	aspartate aminotransferase
BICR	blinded independent central review
BMI	body mass index
BMS	Bristol-Myers Squibb
BOR	best overall response
BP	blood pressure
BSA	body surface area
C	Celsius or Cycle
CFR	Code of Federal Regulations
CI	confidence interval
cm	centimeter
CNS	central nervous system
CPS	combined positive score
CR	complete response
CrCl	creatinine clearance
CRF	case report form
CT	computed tomography
CTLA 4	cytotoxic t-lymphocyte-associated antigen 4

Term	Definition
CYP	cytochrome p-450
D	day
DCR	disease Control Rate
DILI	drug induced liver injury
DLT	dose limiting toxicity
DMC	Data Monitoring Committee
DOR	duration of response
ECG	electrocardiogram
ECOG	Eastern Cooperative Oncology Group
eg	exempli gratia (for example)
eCRF	electronic case report form
eGFR	estimated glomerular filtration rate
FDA	Food and Drug Administration
FDC	fixed dose combination
FFPE	formalin-fixed, paraffin-embedded
FOLFOX	oxaliplatin, leucovorin, and fluorouracil
FSH	follicle stimulating hormone
FU	follow-up
GEJ	gastroesophageal junction
GC	gastric cancer

Term	Definition
HCG	human chorionic gonadotrophin
HCV	hepatitis C virus
HCG	human chorionic gonadotropin
HIV	human immunodeficiency virus
HR	hazard ratio
IA	interim analysis
IB	Investigator's Brochure
IEC	Independent Ethics Committee
Ig	immunoglobulin
IMAE	immune-mediated adverse events
INR	international normalized ratio
IO	immuno-oncology
IP	investigational product
IRB	Institutional Review Board
IRT	Interactive Response Technology
IU	International Unit
IV	intravenous
J	Japan
K	Korea
kg	kilogram
K-M	Kaplan-Meier
L	liter
LAG-3	lymphocyte activation gene 3

Term	Definition
mg	milligram
MHC	major histocompatibility complex
min	minute
mL	milliliter
mAbs	monoclonal antibodies
MI	myocardial infarction
MRI	magnetic resonance imaging
µg	microgram
N/A	not applicable
NCI CTCAE	National Cancer Institute Common Terminology Criteria for Adverse Events
ORR	objective response rate
OS	overall survival
PD	progressive disease
PD-1	programmed death-1
PD-L1	programmed death-ligand 1
PD-L2	programmed death-ligand 2
PET	positron emission tomography
PFS	progression-free survival

Term	Definition
PR	partial response
Q2W	every 2 weeks
Q3W	every 3 weeks
Q4W	every 4 weeks
RECIST	Response Evaluation Criteria in Solid Tumors
RNA	ribonucleic acid
ROW	rest of world
SAE	serious adverse event
SD	stable disease
SI	International System of Units
SOX	S1 and oxaliplatin
T	Taiwan
T3	triiodothyronine
T4	thyroxine
TnI	troponin I
TnT	troponin T
ULN	upper limit of normal
US	United States
VAS	visual analogue scale
WOCBP	women of childbearing potential

Term	Definition
XELOX	capecitabine and oxaliplatin

